1. INTRODUCTION

1.1. Hypothesis

We hypothesize that the sensations associated with chronic cough as captured by the ToPiC questionnaire change following standard treatment for chronic cough. We also hypothesize that these changes correlate with both objective/subjective measures of cough and cough-specific quality of life and that the ToPiC questionnaire will be able to differentiate between those with RCC/UCC and non-RCC/UCC.

2. BACKGROUND

2.1. Prior Literature and Studies

Chronic cough (cough present >8 weeks) is a common problem seen in both primary and secondary care services. It has a significant impact for the individual in terms of quality of life, and for society in terms of healthcare utilisation and loss of productivity.¹ Despite this, few effective therapies for this condition exist and relatively little is known about the impact of these therapies for the individual. Most therapies have been evaluated using subjective cough severity scales (e.g., visual analogue scales [VAS] or numerical Likert scales) or cough related quality of life scores. More recently, with the development of cough monitoring devices (e.g., the VitaloJAK monitor) potential new therapies have been assessed with objective cough rates as an outcome measure.^{2,3}

Refractory Chronic cough and Unexplained Chronic cough (RCC/UCC) are increasingly being recognised as due to a hypersensitivity of the cough reflex, with evidence for both peripheral (at the level of pulmonary vagal afferents) and central sensitisation. Currently the diagnosis is one of exclusion following systematic trials of treatment for other potential causes for cough. However, patients referred to our specialist cough clinic give a characteristic history describing similar sensations (e.g., an 'itch' in the throat) and triggers (e.g., change in atmosphere or temperature) of cough, which is likely related to cough reflex hypersensitivity, and therefore has the possibility of identifying patients with RCC/UCC at an earlier stage and thus those appropriate for novel anti-tussive therapies such as gefapixant.⁴

Our group is therefore developing a validated questionnaire describing the sensations and triggers provoking cough, the ToPiC questionnaire, (see attached copy). Patient interviews and focus groups have been completed and analysed to generate the questionnaire items and an initial long version of the questionnaire developed. Uniquely, this questionnaire has been applied not only to patients with both RCC/UCC but also cough associated with common respiratory diseases including asthma and idiopathic pulmonary fibrosis. This data is currently being used to reduce the number of items in the long questionnaire to those most able to discriminate between cough associated with an underlying disorder (non-RCC/UCC) and RCC/UCC; data on repeatability of these items has also been collected and is StaRR Protocol V4.0 27 September 2023 IRAS 288299 Sponsor no. G73936/B01379

being analysed. This reduced item version will be the ToPiC questionnaire used for the first time in this study. The ToPiC questionnaire is being developed to help identify patients with RCC/UCC at an earlier stage who would be eligible for specific treatment for this condition.

There are several important differences between the TOPIC questionnaire and the Hull Airway Reflux Questionnaire (HARQ)

- The HARQ questionnaire was not developed using currently accepted methodology for questionnaire development. It is a modification of a questionnaire developed by an ENT surgeon (the Reflux Symptom Index, RSI) to diagnose patients with laryngo-pharyngeal reflux. The origin of the original 9 items in the RSI is unclear and the additional 5 items in the HARQ were added following a literature review rather than consulting with patients about their symptoms.
- 2) The HARQ has only be validated to differentiate chronic cough from healthy controls. A questionnaire able to distinguish between RCC/UCC and chronic cough would be much more valuable and relevant to clinical practice. The TOPIC questionnaire has uniquely been developed with this in mind, collecting data from patients with cough associated with asthma, IPF etc. as well as RCC/UCC.
- 3) The HARQ does not differentiate well between healthy controls and chronic cough patients as there was overlap in the scores between these groups. This suggests either some of the healthy controls were not truly healthy or some of the items have poor specificity for chronic cough. Further optimization of the items has not been performed.
- 4) The name of the HARQ implies a role for reflux disease in those scoring highly however the HARQ has never been correlated with any measure of reflux disease. This is confusing and misleading for those not familiar with the field of chronic cough.

The next step in the development of our questionnaire is to apply it to a larger group of patients with chronic cough, to evaluate internal reliability, concurrent validity, and responsiveness to change in patients attending a tertiary cough clinic for the first time. This does not represent a validation study, rather further development and refinement of the ToPiC questionnaire to optimize performance. As approximately

70% of clinic attendees have RCC/UCC we will also start to explore the ability of the questionnaire to discriminate these subjects compared with the 30% with non-RCC/UCC. ^{5,6,7.} This larger dataset will also allow us to explore the possibility of developing a short form of the ToPiC questionnaire e.g. 3-4 items that may be valuable to those working in primary care to allow early identification of possible RCC/UCC patients, facilitating appropriate care such as access to new anti-tussive agents.

3. STUDY OBJECTIVES

3.1. Primary Objective

Whether the triggers and sensations provoking captured by a newly developed questionnaire (ToPiC) change following standard treatment for cough.

3.2. Secondary Objectives

Whether these changes correlate with changes in cough related quality of life and subjective/objective measures of cough in patients referred to a specialist cough clinic

Whether ToPiC questionnaire responses differ between those with refractory (RCC)/unexplained (UCC) chronic cough and those with another cause for cough e.g. asthma (non-RCC/UCC)

3.3. Outcome measures

Primary outcome

Change in ToPiC questionnaire score before and after treatment

Secondary outcome

Correlation between change in ToPiC questionnaire score before and after treatment and changes in (LCQ), cough VAS, verbal cough score and objective cough counts (24hr and mean cough frequency / hour).

4. STUDY DESIGN

4.1. Overview/Design Summary

This study is an observational study involving 100 subjects who are referred as new patients to the specialist cough clinics.

Subjects will be recruited from the specialist Cough Clinics and undergo the following procedures:

Visit 1/Baseline:

- Cough visual analogue scale (VAS) and Verbal (0-10) cough score
- Cough related quality of life questionnaire (Leicester Cough Questionnaire[LCQ])
- ToPiC questionnaire
- 24 hour cough monitoring (VitaloJAK)

Subjects will then undergo investigation and treatment according to the North West Cough Network guidelines which have been developed locally and based upon published guidelines and evidence.

Once the end of the algorithm has been reached and/or cough has reached stability, patients will undergo identical procedures as at baseline. StaRR Protocol V4.0 27 September 2023 IRAS 288299 Sponsor no. G73936/B01379

4.2. Inclusion Criteria

- □ Anyone over the age of 18
- □ Referred to our tertiary chronic cough clinic.
- Non smokers or ex smokers <20 pack years and greater than 6 months abstinence
- □ Persistent cough of at least 8 weeks duration

4.3. Exclusion Criteria

- □ Currently taking angiotensin converting enzyme (ACE) inhibitors
- Recent history of upper or lower respiratory tract infection within 4 weeks of enrolment.
- □ Current smoker or smoking history >20 pack years

All individuals will be considered for inclusion in this study regardless of age, disability, gender reassignment, marriage and civil partnership, pregnancy and maternity, race, religion and belief, sex, and sexual orientation except where the study inclusion and exclusion criteria EXPLICITLY state otherwise.

4.4. Ethical Considerations

We do not believe this study poses any significant ethical issues

4.5. Recruitment and Consent Process

Potential participants will be identified from respiratory clinics by the direct clinical care team members. Prior to the appointment a PIS will be sent to the patient explaining the study. Participants will be able to ask further questions about the study at the time of their appointment from the research staff if they consent to StaRR Protocol V4.0 27 September 2023 IRAS 288299 Sponsor no. G73936/B01379

being approached by them. Written consent will be obtained from patients prior to the completion of questionnaires.

4.6. Associated Risks and Benefits

There are no direct benefits or significant risks to patients taking part in this study. All participants will receive up to £55 per study visit, to compensate them for their time and travel expenses.

4.7. Early Withdrawal of Subjects

As part of the consent process, all participants are informed that taking part is entirely voluntary and that they may withdraw at any time if they wish to do so, without giving any reason. Any data that has already been collected will be retained, but no further trial procedures will be carried out or data obtained.

5. STUDY PROCEDURES

5.1. Screening for Eligibility and first visit

Data Collection: A demographic sheet will be completed by the researcher to collect clinical information about recruited patients (e.g. gender, age, diagnosis, latest clinical spirometry and smoking history).

ToPiC Questionnaire: Participants will be asked to complete the TOPIC Questionnaire. This is a 15 item questionnaire where participants will grade on a likert scale specific sensations and triggers in relation to their cough. This questionnaire was developed as a tool to aid the discrimination of cough in refractory or unexplained chronic cough (RUCC) compared to cough in other respiratory conditions. 100 participants will be requested to complete the questionnaire at visit 1 and visit 2.

Leicester Cough Questionnaire: Participants will be asked to complete the Leicester Cough Questionnaire (cough patients only). This 19 item questionnaire asks subject to grade the impact of their cough on different aspects of their daily life on a scale of 1 to 7. The questionnaire gives a total score and three domain scores: physical, psychological and social effects.

Visual analogue score (VAS) and Verbal Cough Score: The participant will be provided with a visual analogue score (VAS). This is a 100mm line on which they can rate the severity of their cough during the day and night (two separate lines) while wearing the monitor by placing a vertical mark on the line, where 0mm is no cough and 100mm is the most severe cough ever experienced. Separately the patient will also be asked to give a verbal cough score (0-10, with 10 being most severe).

Cough Monitoring: Participants will be fitted with a VitaloJAK ambulatory cough monitor. This will be done at the clinic, the Clinical Research Facility or in certain circumstances, remotely, within 7 days of consent and prior to starting antitussive treatments. If done

remotely, instructions will be provided on how to fit the cough monitor. The patient will also be offered a telephone or video call with a researcher, to guide them through the fitting.

The device will be worn for 24 hours, recording all sound via 2 microphones, one attached to the subject's chest wall and one attached to the subject's clothing. The device will automatically stop recording when the 24 hours has passed. Participants will be made aware that all sound, including speech will be recorded. They will also be informed that the device cannot get wet and therefore they will be unable to shower while wearing it. We will ask participants whether they would be happy to consent to have their recording added to our database of anonymized cough monitor recordings, RaDAR. This is described in more detail in the section data handling and storage of cough recordings. Participants will be asked to either return the cough monitor to the clinic, or in certain circumstances collection will be arranged. Cough monitors are provided by VitaloJak – with provision for maintenance and replacement if needed.

5.2. Follow-up/ Visit 2 (After cough treatment algorithm completed)

The follow up visit will occur at the end of the study. This will be defined as completion of cough algorithm, which will be defined by completion of investigation and treatment or stability of symptoms (not set time for this but estimated to be 6-12 months after visit 1).

All assessments outlined in Section 5.1 will be repeated at this visit. Additionally, medical history in relation to the clinical care of cough will be collected and will include; final diagnosis, treatments tried and any clinical investigations undertaken.

6. SAFETY AND ADVERSE EVENTS

6.1. SAE / AE COLLECTION IN STUDY

We will collect all AEs and SAEs during the study period from consent to the end of the second visit, however this would be unexpected given the nature of the study.

• Safety Reporting

The Manchester University NHS Hospital Foundation Trust R&D will be informed of any incident which may have caused serious injury or death or a serious deterioration in an individual's state of health, by emailing [contact] within 24 hours of becoming aware of the event.

The CI will be responsible for the reporting of related and unexpected Serious Adverse Events (SAEs) to be submitted to the REC. These will be sent within 15 days of the chief investigator becoming aware of the event. All parties will comply with the agreed MFT SOPs for AE and SAE reporting.

7. STATISTICAL PLAN

StaRR Protocol V4.0 27 September 2023 IRAS 288299 Sponsor no. G73936/B01379

7.1. Sample Size and Power Calculation

The investigator and team will be responsible for analyzing the study data.

Variables/Time Points of Interest

The outcomes detailed above will be analyzed at the end of the study following completion of the last study visit.

Statistical Methods

For the primary and secondary endpoints, comparing baseline with post-study measurements, a paired t-test will be used. Should the data be non-parametric, it will be log transformed prior to analysis

For correlations, Pearson (for parametric) and Spearman's (for non-parametric) correlation coefficients will be calculated.

To compare baseline ToPiC scores between RCC/UCC and non-RCC/UCC, an independent-samples t-test will be used. Data will be log-transformed prior to analysis if it is non-parametric.

In order to assess the internal reliability of the ToPiC questionnaire, we will use Cronbach's Alpha test.

Multiplicity

Due to the number of outcomes, a statistical correction should not be required.

Power/Sample Size:

As this is an exploratory study, a sample size of 100 subjects with a complete data set has been selected.

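### The only fallback for non-normal data in the t-tests is a log transformation, which is undefined at the valid zeros of the VAS and verbal score and suits bounded scores only in some shapes

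*Protocol*

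**What the plan says.** Under Statistical Methods in Section 7.1, the protocol states: "For the primary and secondary endpoints, comparing baseline with post-study measurements, a paired t-test will be used". The next sentence gives the fallback: "Should the data be non-parametric, it will be log transformed prior to analysis". For the baseline ToPiC comparison of RCC/UCC with non-RCC/UCC, by independent-samples t-test, it says: "Data will be log-transformed prior to analysis if it is non-parametric". No rank test, added constant or rule for zeros accompanies either statement.

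The correlations are treated differently: "For correlations, Pearson (for parametric) and Spearman's (for non-parametric) correlation coefficients will be calculated".

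Section 5.1 defines the scales. The VAS is a 100 mm line "where 0mm is no cough and 100mm is the most severe cough ever experienced", marked separately for day and night. The other severity rating is a "verbal cough score (0-10, with 10 being most severe". On ToPiC: "This is a 15 item questionnaire where participants will grade on a likert scale specific sensations and triggers"; the item anchors are not given. LCQ items are graded "on different aspects of their daily life on a scale of 1 to 7".

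Section 3.3 defines the primary outcome as the change in ToPiC score. The secondary outcome is the correlation of that change with the changes in LCQ, VAS, verbal score and cough counts.

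**The concern.** One transformation is prescribed for scales that behave differently. A log suits positive, right-skewed quantities such as cough frequency. It has no value at 0, and 0 on the VAS means that the cough has gone. The patients the rule cannot handle on the VAS and verbal score are therefore those with the best outcome. An analyst who reaches this point has to choose between deletion and a constant after seeing the data.

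The rule also reaches the primary endpoint. ToPiC is a bounded sum of Likert items, and a log can make such a score less normal. It also changes the estimand: a test on log scores concerns a ratio of visits, whereas Section 3.3 defines a change in score and correlates changes. At stake are the interpretability of the pre-post estimates and their independence from choices made at analysis.

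**Working it through.** The protocol gives no distribution, SD or effect size, so it has no figure to reproduce. The result at zero is exact. Everything else below rests on assumed inputs.

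**1. Zero on the log scale.** ln(0) is minus infinity, so a Visit 2 score of 0 has no log change. For *n* = 100 (Section 7.1) and an assumed proportion *p* of patients at 0, P(at least one zero) = 1 − (1 − *p*)^100:

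- *p* = 1%: 1 − 0.99^100 = 63%
- *p* = 2%: 1 − 0.98^100 = 87%
- *p* = 5%: 1 − 0.95^100 = 99%

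**2. How far the unstated choice moves the estimate.** Two simulations of the VAS, each with *n* = 100 and 10% of patients at 0 mm at Visit 2:

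- A: baseline mean 60, SD 20; the other patients at 0.5 to 1.1 times baseline.
- B: baseline 100 × Beta(3, 2.2); the other patients at baseline − 4 plus normal noise with SD 20, limited to 1–100.

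| Handling of zeros | Visit ratio, A | Visit ratio, B |
|---|---|---|
| dropped | 0.78 | 0.79 |
| +1 | 0.54 | 0.56 |
| +0.1 | 0.44 | 0.44 |

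A hand check on A: a patient going from 60 to 0 contributes ln(1/61) = −4.11 with +1, and ln(0.1/60.1) = −6.40 with +0.1. Take 0.78 for the other 90%, where ln 0.78 = −0.248:

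- +1: exp(0.9 × −0.248 + 0.1 × −4.11) = exp(−0.635) = 0.53
- +0.1: exp(0.9 × −0.248 + 0.1 × −6.40) = exp(−0.864) = 0.42

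Both are close to the simulated values. The gap between the rows comes from the constant, not from the patients.

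**3. Whether the log repairs normality.** Mean skewness of the paired VAS differences in B, with the share of runs in which a Shapiro–Wilk test at 5% rejects normality of the raw differences (the protocol names no test):

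| Zeros | Raw | log(x+1) | Log, zeros dropped | Raw rejected |
|---|---|---|---|---|
| 5% | −0.60 | −2.43 | −2.46 | 61% |
| 10% | −0.74 | −1.95 | −2.43 | 82% |

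Under these inputs the zeros themselves often trigger the fallback, and the fallback then makes the departure larger.

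**4. Bounded scores at one visit.** Skewness before and after the log, for assumed shapes. The ToPiC ranges assume 15 items scored 0–4 or 1–5; the LCQ total is assumed to run 3–21.

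| Raw shape | 0–60 (zeros left out of the log) | 15–75 | LCQ 3–21 |
|---|---|---|---|
| symmetric | 0.0 to −1.45 | 0.0 to −0.60 | 0.0 to −0.70 |
| left-skewed | −0.47 to −1.45 | −0.47 to −1.01 | −0.47 to −1.08 |
| right-skewed | 0.47 to −1.08 | 0.47 to −0.14 | 0.47 to −0.26 |

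The log clearly helps only for right skew with a minimum above 0. With stronger right skew on 0–60 (0.86) it gives −0.73, which mainly reverses the sign. For lognormal data, a plausible model for cough counts, skewness goes from 5.6 to 0.0, so there the log is appropriate.

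**5. Meaning of change.** Under the fallback the paired test estimates mean[ln(Visit 2) − ln(Visit 1)], a ratio when exponentiated. The correlations use Spearman with no log. Sections 3.3 and 7.1 would then carry two definitions of change.

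**The case against.** The strongest reply is that the rule is conditional and the damage limited. A mildly skewed ToPiC score would often not trigger it: a skewness of −0.32 with 100 patients is about 1.3 standard errors, taking √(6/100) ≈ 0.24. A paired t-test on about 100 pairs tolerates moderate skewness, so extra skewness after a log does little harm to its validity. The normality check and any constant could be set out in an SAP that is not shown, and the protocol does not say that normality is judged on raw scores rather than differences. No passage supports 10% of patients at 0 mm. The study is described as exploratory and not a validation study.

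Much of this stands. It limits the severity and makes the figures above illustrations only. It does not rescue the rule. The protocol itself prescribes the log and makes it the only fallback for the t-tests, so this is a stated choice and not a detail left open. A constant set later would make the VAS and verbal score computable, but the ratio would still depend on its value. Robustness of the t-test argues for leaving the scores untransformed.

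A reader might infer that the rule covers every analysis, or that it breaks the primary endpoint at zero. The documents do not support either. The correlations, which are the secondary outcome named in Section 3.3, fall back to Spearman. The VAS, verbal score, LCQ and cough counts meet the log only through the pre-post tests that Section 7.1 adds. LCQ items start at 1, so that score cannot be 0. The ToPiC anchors are not given, so a zero there is possible but not shown. The group comparison uses baseline scores in patients with persistent cough, so loss of responders does not arise there.

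**Conclusion.** The point holds in a limited form. Once triggered, the fallback is undefined for any VAS or verbal score of 0, both valid values, and for any cough count of 0 should one occur. Handling those patients requires a choice that the protocol does not make. With 10% zeros assumed, that choice moves the visit ratio from about 0.78 to 0.55 or 0.44, an apparent reduction of 22%, 45% or 56% from the same patients.

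For ToPiC and LCQ the problem is suitability and meaning, not failure at zero. The log worsens left-skewed scores and can help right-skewed ones with a minimum above 0. It also replaces the defined change in score by a ratio. Which shape ToPiC has is unknown from the documents.

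This should be fixed before analysis. It is not a fatal flaw: the study is exploratory, the fallback is conditional, and the sizes rest on assumed distributions. The independent-samples t-test for the group comparison is not itself an error.

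**What to change.** Amend Statistical Methods in Section 7.1 as follows:

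- **ToPiC, LCQ, VAS and verbal score:** analyse the untransformed paired difference with a paired t-test and 95% CI. Judge normality on the differences. Use the Wilcoxon signed-rank test or a bootstrap CI as the fallback.
- **Baseline ToPiC by group:** keep the t-test, with Mann–Whitney as the fallback in place of the log.
- **Cough frequency:** keep the log, with one rule for zeros fixed before the data are seen.
- **Change:** use the same definition of change for each measure in the pre-post test and in the correlations.

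This agrees with the rank-based fallback the protocol already accepts for correlations. The cost is a wording change, with no new data or visits. The downside is that a signed-rank test gives a less direct estimate of the mean change; the bootstrap CI avoids this where the mean is wanted.

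### The t-test named for RCC/UCC versus non-RCC/UCC answers whether scores differ, but does not estimate how well ToPiC differentiates the groups; an AUC with its confidence interval would

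*Protocol*

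**What the plan says.** The protocol puts the question in two ways.

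- **Differentiation.** Section 1.1 hypothesises that "the ToPiC questionnaire will be able to differentiate between those with RCC/UCC and non-RCC/UCC". Section 2.1 gives the purpose of the questionnaire as picking out patients with RCC/UCC sooner, and says of this study that "we will also start to explore the ability of the questionnaire to discriminate these subjects compared with the 30% with non-RCC/UCC". Section 5.1 likewise describes ToPiC as an aid to discriminating RCC/UCC from cough in other respiratory conditions.
- **Difference.** The secondary objective in section 3.2 is narrower: "Whether ToPiC questionnaire responses differ between those with refractory (RCC)/unexplained (UCC) chronic cough and those with another cause for cough".

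For the analysis, section 7.1 states: "To compare baseline ToPiC scores between RCC/UCC and non-RCC/UCC, an independent-samples t-test will be used", with log transformation if the data call for it. It names no AUC, ROC curve, sensitivity, specificity or cut-off, and neither does any other section. The outcome measures in section 3.3 do not mention the comparison. Section 7.1 calls the study exploratory and gives no significance level, effect size or SD; on size it says only that "a sample size of 100 subjects with a complete data set has been selected". Section 2.1 states that this is not a validation study.

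**The concern.** A t-test asks whether two group means are equal. Differentiation concerns individuals: how often a patient with RCC/UCC scores higher than one without, and how many patients a cut-off would classify correctly. A p-value answers neither question. With enough patients, a small shift in mean is significant even when the two distributions lie almost on top of each other.

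What is at stake is how the result can be read. If the analysis stops at the named test, a significant result would leave the section 1.1 hypothesis unquantified, and a reader could not tell weak separation from useful separation. A non-significant result would be just as uninformative about how much discrimination had been excluded.

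**Working it through.** The protocol gives no power or effect-size figure to reproduce, so the check asks what a just-significant t-test implies about discrimination.

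**Inputs from the protocol**
- N = 100 with complete data (section 7.1).
- About 70% RCC/UCC and 30% non-RCC/UCC among clinic attendees (section 2.1), hence 70 and 30 patients.

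**Assumptions not in the protocol**
- Two-sided 5% level.
- Normal scores with equal variances. If scores are log-transformed, the SD figures apply on that scale. The AUC itself is unchanged by any monotone transformation.

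**Step 1: smallest significant difference, in SD units**

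d = t(0.975; 98) × √(1/70 + 1/30) = 1.984 × 0.2182 = 0.433

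**Step 2: what that difference means for discrimination**
- AUC = Φ(d/√2) = Φ(0.306) = 0.62
- Overlap = 2Φ(−d/2) = 2Φ(−0.2165) = 0.829, about 83%
- Sensitivity = specificity at the midpoint cut = Φ(d/2) = 0.586
- At 70% prevalence, PPV = 0.7 × 0.586 / (0.7 × 0.586 + 0.3 × 0.414) = 0.77. Labelling every attendee RCC/UCC already gives 0.70.
- NPV = 0.3 × 0.586 / (0.3 × 0.586 + 0.7 × 0.414) = 0.38

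**Step 3: sensitivity to the split, same method**

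| Split | d | Overlap | AUC |
|---|---|---|---|
| 50/50 | 0.397 | 84.3% | 0.61 |
| 60/40 | 0.405 | 83.9% | 0.61 |
| 70/30 | 0.433 | 82.9% | 0.62 |
| 80/20 | 0.496 | 80.4% | 0.64 |

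The conclusion does not depend on the exact split.

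**Step 4: away from the boundary**

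The true difference detectable with 80% power (normal approximation) is (1.960 + 0.842) × 0.2182 = 0.611 SD. This gives an AUC of 0.67 and 76% overlap. In the other direction, an AUC of 0.80 needs d = √2 × Φ⁻¹(0.80) = 1.19 SD, with 55% overlap. Significant results therefore span weak to good discrimination, and the p-value does not say which has been found.

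**Step 5: precision of an AUC at 70 versus 30 (Hanley–McNeil)**

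For A = 0.75: Q₁ = A/(2 − A) = 0.600 and Q₂ = 2A²/(1 + A) = 0.643.

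SE² = [A(1 − A) + 69(Q₁ − A²) + 29(Q₂ − A²)] / (70 × 30) = (0.1875 + 2.5875 + 2.330) / 2100 = 0.00243

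SE = 0.0493, so the 95% half-width is 1.96 × 0.0493 = 0.097. The same formula gives about 0.59 to 0.81 at an AUC of 0.70 and 0.71 to 0.89 at 0.80. That is informative enough for exploratory work.

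**The case against.** The strongest reply is that the test is right for its objective. Section 3.2 asks whether responses differ, and a two-sample comparison answers that. The protocol also limits its own ambition: it is exploratory, is not a validation study, only begins to look at discrimination, and does not list discrimination among the outcomes in section 3.3. ROC detail could reasonably sit in a SAP that is not shown. All of this stands, and it limits the weight of the point. It does not remove it, because section 1.1 hypothesises differentiation and section 7.1 positively names a method that does not measure it. A SAP that simply followed section 7.1 would inherit the gap.

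A reader might infer several stronger things that the documents do not support.

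- *That the t-test is wrong, or that the study will declare differentiation on p < 0.05.* The protocol sets no success rule and no significance level for this comparison.
- *That 83% overlap is what the study will find.* It is the value at exactly p = 0.05. A large observed difference would imply good separation under the same model.
- *That ToPiC is held to a lower bar than the HARQ.* Section 2.1 does say "The HARQ does not differentiate well between healthy controls and chronic cough patients as there was overlap in the scores between these groups", but that contrast is between healthy people and coughers. ToPiC's contrast is between two groups of coughers, and the protocol does not adopt overlap as a pass mark.
- *That the possible 3–4 item short form will be reported with inflated accuracy.* Section 2.1 only mentions exploring the possibility. It fixes no selection method and plans no performance claim, so no amount of optimism can be derived from the document.

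It is also fair to say that an AUC without a minimum acceptable value does not raise the bar by itself. At the boundary of significance the AUC interval is about 0.50 to 0.74, so it too only just excludes 0.5. The gain is that weak discrimination becomes visible in the report.

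**Conclusion.** The point holds as a mismatch between the hypothesis and the named analysis. The t-test serves the section 3.2 objective, but on its own it does not estimate the differentiation that section 1.1 hypothesises. At 70 versus 30, a just-significant result is compatible with an AUC of about 0.62, about 83% overlap, and sensitivity and specificity of about 59% at the midpoint. This rests on a two-sided 5% level, normality and equal variances, and it is a boundary case. Across splits from 50/50 to 80/20 the overlap at the boundary stays between 80% and 84%. Because the study is exploratory and makes no validation claim, this is an inexpensive improvement to the analysis and its interpretation. It does not threaten the primary objective.

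**What to change.** In the Statistical Methods part of section 7.1:

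1. Add the ROC AUC of the baseline ToPiC score, with RCC/UCC status taken from the Visit 2 final diagnosis, and its 95% CI, as the exploratory estimate of discrimination. Name the Visit 2 diagnosis explicitly, because section 5.1 and the Appendix also record a diagnosis at Visit 1.
2. Report sensitivity and specificity descriptively.
3. Keep the independent-samples t-test for the section 3.2 objective.
4. State that any conclusion that ToPiC differentiates the groups will rest on the AUC and its interval, not on the t-test p-value.

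If only a difference in mean score is intended, the alternative is to reword the hypothesis in section 1.1 to match section 3.2.

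The cost is a few sentences and a little more analysis. Baseline ToPiC (section 5.1) and the final diagnosis (section 5.2) are already collected. The downside is that the result may look less favourable than a bare p-value, with an interval of about ±0.10 at an AUC of 0.75.
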